12.0 Participant Information

12.1 Subject Population:

The target population is ALL pregnant women within the San Antonio Military Community, receiving their OB orientation and prenatal care at the Brooke Army Medical Center (BAMC). Military prenatal services are now consolidated and provided at BAMC. The San Antonio military population includes Air Force, Army, Navy, and Marine active-duty servicewomen, retired service women, and female military beneficiaries of active duty, and retirees. The intent is to generalize the findings to all military branches, recognizing that some of the branches may not have broad sampling within this location. On-going studies/data collection at 3 other military installations will provide baseline data for comparisons. The findings may be extrapolated to pregnancy in general.

All women attending OB orientation have had their pregnancies verified through the OB clinic. Therefore, additional screening is not required to confirm they are pregnant. The study inclusion criteria includes, being a pregnant woman, in the first trimester, Active Duty or a DoD beneficiary. The women may also be participants in the Mentors Offering Maternal Support study at BAMC.

12.2 Age Range:

Check all the boxes that apply. If the age range of potential subjects (specimens, records) does not match the range(s) selected, please specify in the text box.

18-24
 25-34
 35-44
 45-54
 55-64
 65-74
 75+

12.3 Gender:

Male
 Female
 Other

12.4 Special categories, check all that apply

Minors /Children
 Students
 Employees - Civilian
 Employees - Contractor
 Resident/trainee
 Cadets /Midshipmen
 Active Duty Military Personnel
 Wounded Warriors
 Economically Disadvantaged Persons
 Educationally Disadvantaged Persons
 Physically Challenged (Physical challenges include visual and/or auditory impairment)
 Persons with Impaired Decisional Capacity
 Prisoners
 Pregnant Women, Fetuses, and Neonates
 Non-English Speakers
 International Research involving Foreign Nationals - Headquarters Review is necessary

12.5 Inclusion Criteria:

Order Number	Criteria
1	Inclusion: Prima or multigravida; 1 st trimester of pregnancy at consent; \geq 18 years old; wife or DoD beneficiary (Active Duty or retiree) partner to a military service member or retiree or a DoD beneficiary member (Active Duty, retiree). If the pregnant woman is not a DoD or TRICARE beneficiary, than Secretarial Designee (SECDES) status approval must be obtained in order for her to be eligible to participate in the research study, based on DoDI 6025.23.

12.6 Exclusion Criteria:

Order Number	Criteria
1	Exclusion: Anticipated permanent change of station during study; dependent daughter of active duty or retired military member; $>$ 12 weeks gestation at consent; $<$ 18 years of age; inability to understand or speak English; non-sponsored DoD members (civilians).

13.0

Recruitment and Consent

13.1 Please describe the recruitment process, including how subjects will be identified and selected for the study.

The study inclusion criteria includes, being a pregnant woman, in the first trimester, Active Duty or a DoD beneficiary. The women may also be participants in the Mentors Offering Maternal Support study at BAMC. All women attending OB orientation have had their pregnancies verified through the OB clinic. Therefore, additional screening is not required.

Identification of participants will occur in the following ways:

1) Women entering OB care within the first trimester of pregnancy (≤ 12 weeks) will be introduced to the study by research team members in person or by phone. For those women indicating interest in participating they will be provided the study information, a review of the inclusion/exclusion criteria for participation and the informed consent documents.

2) Women who are not contacted by phone may be met in person during OB orientation to discuss the study or have the option of setting up another more convenient time to meet with the research team members.

3) Potential participants may also be accessed in the OB clinic after the OB orientation appointment if they express a desire to hear more about the study/meet with a team member. If the patient does not have time to stay after the OB orientation to meet with a study member they may elect to complete the Inclusion/Exclusion screening form with contact information and the research team members will follow-up with a phone call.

4) Potential participants will also be given the option to receive their ICD and HIPAA documents via email form which will be signed by wet signature or electronically signed and returned to a research team member who will review the ICD and the HIPPA forms.

a) Each electronic signature will have a date stamp incorporated with it at the time of signature.

[NOTE: without a date stamp, the electronic signature is not valid]

b) The investigator will have some means to personally verify the subject's identification, e.g., compare with a State-issued or government-issued ID; a driver's license; use of personal security questions; etc. This must be done BEFORE the investigator sanctions the acceptance of an individual's electronic signature. [The investigator must state the means of verification in their research files for audit purposes.]

c) After the research team member administering the consent, signs and dates the ICD, a copy of the signed ICD will be given to the subject. The ICD and HIPPA form will be signed prior to any data collection.

Once consented, the participant will then be asked to complete the first study booklet. If the participant chooses to review/complete the study documents at home rather than at their appointment they can complete them, through the web-based, Qualtrics system, specifically designed for collecting anonymous research content.

Participation in the study is a voluntary activity. Every participant indicating a desire to participate in the study will be consented in person prior to completion of any study documents or interview. The time and place of consent will vary depending on the means of recruitment (see options above). If the participant is recruited in person, then the consent process can be conducted at the same time. However, if the participant has called indicating interest in the study or been recruited through a phone call, determination is made between the study staff and participant regarding an appropriate process to review/sign the consent documents.

13.2 Compensation for Participation:

There is no compensation.

13.3 Please describe the pre-screening process. If no pre-screening, enter Not Applicable in the text editor

Note that all women attending OB orientation have had their pregnancies verified. Additional screening for pregnancy is not required. Determination of the Inclusion/Exclusion criteria will be made with the screening form (see attachment form).

13.4 Consent Process:

Revised Common Rule, Section 219.116: General requirements for informed consent, whether written or oral, are set forth in this paragraph and apply to consent obtained in accordance with the requirements set forth in paragraphs (b) through (d) of this section. Broad consent may be obtained in lieu of informed consent obtained in accordance with paragraphs (b) and (c) of this section only with respect to the storage, maintenance, and secondary research uses of identifiable private information and identifiable biospecimens.

Are you requesting a waiver or alteration of informed consent?

Yes No

Please explain the consent process:

Consenting will occur in the following ways:

1. Potential participants will be consented by a research team member in a private area located in the OB /Gyn clinic. The participant will be provided the study information and if the patient is interested in participating in the study, they will be given the Informed Consent Document and HIPAA Authorization Documents (mother and infant) for review and signature. The ICD's (mother and infant) will be signed authorizing participation in the study. The research team member will review the forms with the patient. Both forms must be signed before any study-related data collection occurs. The participant will be given copies of the signed documents. Potential participants have the option to discuss with family members prior to signing consent documents.

2. Potential participants will also be given the option to receive their ICD and HIPAA documents via email form which will be signed by wet signature or electronically signed and returned to a research team member who will review the ICD and the HIPPA forms.

a) Each electronic signature will have a date stamp incorporated with it at the time of signature.
[NOTE: without a date stamp, the electronic signature is not valid]

b) The investigator will have some means to personally verify the subject's identification, e.g., compare with a State-issued or government-issued ID; a driver's license; use of personal security questions; etc. This must be done BEFORE the investigator sanctions the acceptance of an individual's electronic signature. [The investigator must state the means of verification in their research files for audit purposes.]

c) After the research team member administering the consent, signs and dates the ICD, a copy of the signed ICD will be given to the subject. The ICD and HIPPA form will be signed prior to any data collection.

Once consented, the participant will then be asked to complete the first study booklet. If the participant chooses to review/complete the study documents at home rather than at their appointment they can complete them, through the web-based, Qualtrics system, specifically designed for collecting anonymous research content.

13.5 DoDI 3216.02 requires an ombudsman to be present during recruitment briefings when research involves greater than minimal risk and recruitment of Service members occurs in a group setting. If applicable, you may nominate an individual to serve as the ombudsman.

N/A
 Propose ombudsman

13.6 Withdrawal from Study Participation:

Explain the process for withdrawal and specify whether or not the subjects will be given the opportunity to withdraw their data their data/specimens in the event they wish to withdraw from the study

Participants are free to withdraw at any time. The decision to withdraw will not affect subjects' ability to receive medical care and will not be penalized or lose any benefits to which the subject would otherwise be entitled. If a subject withdraws from the study, all the associated data and tissue samples will be destroyed.

14.0 **Risks and Benefits**

14.1 **Risks of Harm:**

Identify all research-related risks of harm to which the subject will be exposed for each research procedure or intervention as a result of participation in this study. Consider the risks of breach of confidentiality, psychological, legal, social, and economic risks as well as physical risks. Do not describe risks from standard care procedures; only describe risks from procedures done for research purposes

There is minimal risk for participating in this study. Personal information (the questionnaire booklets and demographic data) are securely maintained on a password protected computer with a secured study folder. The paper documents will be locked in a file cabinet in the private secured office of the nurse researcher. Only members of the research team, listed on the research protocol, will have any access to the information. The demographic information will be entered into an electronic spreadsheet that is password protected. The data from the questionnaire booklets and the placental tissue data are entered into a computer data program with no identifiable information. This program is also password protected. At the conclusion of the study, all documents will be shredded. The slides and tissue biopsies will be destroyed unless the research subject consents to maintain the placenta tissue and research data in a data/tissue repository.

Participants could experience emotional distress or anxiety that may affect their well-being or their unborn infant. There may be feelings of isolation, particularly if one's husband/partner is away. No inducements, monetary or otherwise, will be offered to terminate a pregnancy [45 CFR 46.204(h)]. Individuals engaged in the research will have no part in any decisions as to the timing, method, or procedures used to terminate a pregnancy [45 CFR 46.204(i)]. Individuals engaged in the research will have no part in determining the viability of a neonate [45 CFR 46.204(j)].

The Principal Investigator and members of the research team are not the research participant's healthcare provider. Participants will be informed to always notify their provider or nurse in the obstetrical clinic immediately if they need help.

14.2 **Measures to Minimize Risks of Harm (Precautions, safeguards):**

For each research procedure or intervention, describe all measures to minimize and/or eliminate risk of harms to subjects and study personnel

A copy of the consent will be stored by the investigator in a locked file cabinet in a locked office, as part of the research record. All information about the participant, collected on this study, will be kept in an electronic database, which will be double password-protected, firewall-protected, and access-restricted to people involved in this study. [name], the co-investigator will not have access to this dataset until which time the CRADA is signed and in place. As soon as possible, any link between identity and the research information will be destroyed which means research information about the participant will be permanently de-identified. Personal identifying information and identifiable bio-specimens will be destroyed no later than at the closure

of the study. The research information and bio-specimens collected will not be used for any additional research activity beyond what has been described in the consent.

All bio-specimens kept at the *59 MDW, BAMC or University of the Incarnate Word* will be handled and disposed of in accordance with Federal regulations and local laboratory procedures. In accordance with the authorization within the patient consent, once the tissue has been analyzed and run, one of three things will occur, 1) tissue will be destroyed, 2) the tissue will be maintained as a coded specimen within a tissue repository at CAMD, and/or 3) coded slides will be maintained for medical student use at UIW, School of Medicine.

Histology slides for review by [name] will be packed by the PI and/or pathology resident on the study in accordance with bio-specimen requirements. The histology slide samples will be coded and transported from BAMC pathology to UIW School of Medicine at Brooks-City-Base, TX.

All coded stored as a part of the CAMD Data/Tissue Repository for the purposes of this study - (FWH20130092H) at the *Center for Advance Molecular Detection (CAMD) at Joint Base San Antonio Lackland* and will be handled and disposed of in accordance with Federal regulations upon termination of the repository. No individual, investigator, institution or agency will have access to this database without permission of the PI or Repository Manager, *[name]*, and where applicable, the 59 MDW Institutional Review Board (IRB).

The Repository Manager, [name], is responsible for all PHI and PII data stored in the repository. Only de-identified data (data that meets the HIPAA standards for removing direct identifiers or information) will be released to investigators with an IRB-approved research study, so tracing specific information back to the donor of the data should not be possible. Recipient investigators may only receive limited data sets under a Data Use Agreement (DUA) including the information necessary to conduct their IRB-approved research. All recipient investigators requesting data from the repository must have approval from the Repository Manager and must have a research study approved through a DoD Institutional Review Board (IRB) and/or the 59 MDW IRB.

Once the data is collected, an individual's data will not be released or shared with anyone outside the project. Pregnancy and birth outcomes data will be collected from the participant's prenatal record via the electronic medical record. All participants will complete a HIPAA form in addition to the consent form indicating their knowledge of the study personnel obtaining this outcome data from their medical records. Research coordinators, PIs, AIs will complete CITI training and HIPAA training. The procedures outlined above will be covered during team orientation and included within the study binders. Participant questionnaire booklets will be shredded once all the data has been entered into the database twice, cleaned and verified for correctness. Participant log (key) will be needed until all final reports are completed and then shredded.

14.3

Confidentiality Protections (for research records, data and/or specimens):

Describe in detail the plan to maintain confidentiality of the research data, specimens, and records throughout the study and at its conclusion (e.g., destruction, long term storage, or banking). Explain the plan for securing the data (e.g., use of passwords, encryption, secure servers, firewalls, and other appropriate methods). If data will be shared electronically with other team members/collaborators outside the institution, describe the method of transmission and safeguards to maintain confidentiality. Explain whether this study may collect information that State or Federal law requires to be reported to other officials or ethically requires action, e.g., child or spouse abuse

There is the potential risk for loss of confidentiality, although every effort will be made to protect participant confidentiality.

The research team will secure the ICD, HIPAA and any study related documents as indicated above. When recruiting, no items will be left unattended, and all consent items will be maintained in envelopes. Participant consents will be scanned into a separate password-protected file from all other study data and submitted to the IRB annually. The paper copies of all the participant consents will be scanned at the study site into a password-protected file, separate from all other study data, and paper copies of participant consents will be shredded. Personal information are securely maintained on a password protected computer with a secured study folder. Documents will be locked in a file cabinet in the private secured office of the nurse program coordinator. Only members of the research team, listed on the research protocol, will have any access to the information. The demographic information will be entered into an electronic spreadsheet that is password protected. The data from the questionnaire booklets and the placental tissue data are entered into a computer data program with no identifiable information. This program is also password protected. At the conclusion of the study, all documents will be shredded.

Participants could experience emotional distress or anxiety that may affect the well-being of themselves or their unborn infant. There may be feelings of isolation, particularly if one's husband/partner is away. It is expected that some participants will have unexpected terminations of their pregnancy. All events that are life-threatening or fatal will be reported within 24 hours. Any other possible adverse events (expected or unexpected) will be reported to the local IRB as well as the governing IRB at BAMC and at the WHASC according to their guidelines.

See section 14.2 for additional information.

14.4 Potential Benefits:

Describe any real and potential benefits of the research to the subject and any potential benefits to a specific community or society

If the individuals in the research are considered experimental subjects (per 10 USC 980), and they cannot provide their own consent, the protocol must describe the intent to directly benefit all subjects

As the number of women serving in the military increases, it is particularly important to understand the relationship between mental health during pregnancy and its complications leading to poor birth outcomes. There is no guarantee or promise that the subjects will receive any personal benefit from this study. We hope the information learned from this study may help future patients. All the women in the study will be aware that the findings as applicable will be used to update the VA/DoD Clinical Practice Guideline for Pregnancy Management and as norming data for assessment tools used within the DoD.

14.5 Privacy for Subjects:

Describe the measures to protect subject's privacy during recruitment, the consent process, and all research activities, etc.

Potential participants will be consented by a research team member in a private area or if emailed for electronic signature, a) Each electronic signature will have a date stamp incorporated with it at the time of signature. [NOTE: without a date stamp, the electronic signature is not valid] b) The investigator will have some means to personally verify the subject's identification, e.g., compare with a State-issued or government-issued ID; a driver's license; use of personal security questions; etc. This must be done BEFORE the investigator sanctions the acceptance of an individual's electronic signature. [The investigator must state the means of verification in their research files for audit purposes.] c) After the research team member administering the consent, signs and dates the ICD, a copy of the signed ICD will be given to the subject. The ICD and HIPPA form will be signed prior to any data collection.

The research team will review the ICD and HIPAA Authorization forms with the patient. Both forms must be signed before any study-related data collection occurs, including pre-screening procedures to verify inclusion/exclusion criteria for study participation. The participant will be given copies of both documents (ICD for placental study, and the HIPPA form). Additionally, the mother will be given a Parental ICD and a Parental HIPAA Authorization for signature, authorizing her infant to be part of the study and to permit the investigators to access the infant's medical record for birth and infant outcome data. Once consented, the participant will then be asked to complete the first study booklet. If the participant chooses to review/complete the study documents at home rather than at their appointment they can complete them, through the web-based, Qualtrics system, specifically designed for collecting anonymous research content.

The research team will secure the ICD, HIPAA and any study related documents in an envelope that is kept with the research team at all times; no items will be left unattended. Participant consents will be scanned into a separate password-protected file from all other study data and submitted to the IRB annually. The paper copies of all the participant consents will be scanned at the study site into a password-protected file, separate from all other study data, and paper copies of participant consents will be shredded.

Personal information are securely maintained on a password protected computer with a secured study folder. Documents will be locked in a file cabinet in the private secured office of the nurse researcher. Only members of the research team, listed on the research protocol, will have any access to

the information. The demographic information will be entered into an electronic spreadsheet that is password protected. The data from the questionnaire booklets and the placental tissue data are entered into a computer data program with no identifiable information. This program is also password protected. At the conclusion of the study, all documents will be shredded. The slides and tissue biopsies will be destroyed unless the participant consents to maintaining the placenta tissue and research data in a data/tissue repository.

14.6 Incidental or Unexpected Findings:

Describe the plan to address incidental findings and unexpected findings about individuals from screening to the end of the subject's participation in the research. In cases where the subject could possibly benefit medically or otherwise from the information, state whether or not the results of screening, research participation, research tests, etc., will be shared with subjects or their primary care provider. State whether the researcher is obligated or mandated to report results to appropriate military or civilian authorities and explain the potential impact on the subject

Complete confidentiality cannot be promised, particularly for active duty personnel, because information regarding potential UCMJ violations or concerns regarding fitness for duty may be reported to appropriate medical, law enforcement, or command authorities. If an investigator feels at any time that a participant is at risk of self-harm, the participant will be given a direct referral to a provider within the Mental Health Services and their provider notified. Complete confidentiality for active duty pregnant women cannot be guaranteed. Importantly, Mental Health Service appointments do not have any connection with the study or participation in the study.

No blood will be taken as a part of this study. The afterbirth (the placenta) will be sent to pathology for examination as part of this study. If the subject is wanting to obtain the placenta following birth, it can still be requested and obtained through pathology, in the same manner it would be obtained if they were not in this study. If a placental examination is requested by the physician following delivery, this can and will take place regardless of whether participating in the study.

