Pregnancy and neonatal outcome data including gestational age at delivery, infant birthweight, mode of delivery, and pregnancy complications, including pre-eclampsia, gestational hypertension, gestational diabetes, and perinatal and neonatal infections, will be collected from the maternal and infant medical records. If missing from the demographic data form, maternal parity, gestational age at first prenatal appointment, ethnicity, beneficiary status (active duty vs. dependent), smoking history, and other medical history will be obtained from the obstetrical record. The participants have signed a HIPPA form as part of the MOMS study and all data mentioned is being collected as a part of this study.

11.2 Sample Size:

1200

11.3 Total number of subjects requested (including records and specimens):

1200

11.4 If you are recruiting by study arm, please identify the arms of the study and how many subjects will be enrolled in each arm

N/A

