Statistical Analysis System (SAS) version 9.4 will be used for all analyses. Descriptive statistics (mean, sd, median for each continuous variable and proportions for each discrete variable) will be used to describe the sample. Linear or generalized linear mixed models will be developed for all variables, prenatal anxiety, self-esteem, family adaptability/cohesion, prenatal depression and perceived support, as well as the protein and RNA values, in order to examine their association with placental metrics across pregnancy. The linear (mixed) model will be used for all normally distributed continuous data. In the case of skewed continuous outcome data, the generalized linear (mixed) model with gamma distribution and log-link will be chosen. For binary or dichotomized outcomes, a mixed model logistic regression will be chosen. Measurement times (dates of data collection by gestational age), will be included in the models as predictors when available with and without adjusting for the participant's age, employment status, prior deliveries, marital/partner status, education, deployment of partner during pregnancy, military branch of service of participant or partner, ethnicity, military rank of participant or partner and MOPS group. In the case of dual military couples, the rank and service of the active duty woman will be used. The final models will be determined with backward elimination procedure. Timing of data collection (weeks gestation), may also be chosen as a random effect within the model. Additionally, each prenatal variable (prenatal anxiety, self-esteem, depression, family adaptability/cohesion and resilience) will be longitudinally regressed on measurement time to obtain the slope through best linear unbiased predictor (BLUP). The resulted individual slopes will be used to determine any significant effects for prenatal psychosocial scores to pregnancy complications, birth and infant outcomes, and to the physiologic data (both placental scores and biomarker data).

To examine if anxiety mediates the relationship between biomarkers and birth outcomes, we will develop a Baron and Kenny (1986) mediation model assess the relationships as in Bauer and Preacher (2006). We will conduct three mixed regression models adjusted for all appropriate covariates:

1. Regress birth outcome on biomarker.
2. Regress birth outcome on biomarker and anxiety.
3. Regress anxiety on biomarker.

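### Multiple pregnancies are eligible, but plurality is neither a listed data item nor a named covariate, which leaves the birth-outcome models exposed to extra variance and possible confounding

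*Protocol*

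**What the plan says.** Inclusion (section 12.5) opens with "Prima or multigravida; 1 st trimester of pregnancy at consent". Gravidity counts pregnancies, not fetuses, so this places no limit on plurality. The exclusions (section 12.6) begin "Anticipated permanent change of station during study; dependent daughter of active duty or retired military member" and go on to gestation beyond 12 weeks, age under 18, lack of English and non-sponsored civilians. Multiple gestation is not among them. Section 12.1 confirms the breadth: "The target population is ALL pregnant women within the San Antonio Military Community". Section 9.5 says the same.

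The outcome data in sections 10.1 and 11.1 include "gestational age at delivery, infant birthweight, mode of delivery" and a list of complications. Neither section lists the number of fetuses.

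In section 11.6 the models are run with and without "adjusting for the participant's age, employment status, prior deliveries, marital/partner status, education, deployment of partner during pregnancy", followed by military branch, ethnicity, rank and study group. Then: "The final models will be determined with backward elimination procedure". The individual psychosocial slopes are related to complications, birth and infant outcomes, placental scores and biomarkers. For the mediation analysis the wording is looser: "We will conduct three mixed regression models adjusted for all appropriate covariates", with no covariate named.

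**The concern.** Preterm birth and low birthweight are the stated rationale of the study (section 9.2), and purpose 3 (section 9.3) concerns pregnancy, birth and infant outcomes. Plurality is a strong determinant of both gestational age and birthweight, for reasons that have nothing to do with a mother's anxiety. A small group of women with a very different outcome distribution adds variance to every birth-outcome model. If those women also score differently on anxiety, part of any anxiety-outcome association would really be a plurality effect.

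The analysis as written cannot put this right. Backward elimination only removes candidates, and plurality is never a candidate. The number of prior deliveries is a different variable and does not stand in for it.

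A second gap follows. The protocol does not say how a second infant, or a second placenta, of one mother is analysed.

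**Working it through.** **There is no figure in the plan to reproduce on this point.** The sample size of 1200 (section 11.5) rests on a 45% placental pathology rate and states no effect size. It does not bear on plurality. The only preterm rate in the protocol is the worldwide figure of 1 in 10 babies (section 9.2).

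**Assumptions (none from the protocol).** Share of pregnancies that are multiple, t = 1-3.5%, or 12-42 of 1200 women. Preterm rate in multiples, pm = 40-60%. Preterm rate in singletons, ps = 8-10%.

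**Step 1. Share of preterm pregnancies that are multiple** = t·pm / [t·pm + (1 − t)·ps]

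- t = 1%, pm = 40%, ps = 10%: 0.0040 / (0.0040 + 0.0990) = 3.9%
- t = 1.5%, pm = 50%, ps = 10%: 0.0075 / (0.0075 + 0.0985) = 7.1%
- t = 3.5%, pm = 60%, ps = 8%: 0.0210 / (0.0210 + 0.0772) = 21.4%

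**Step 2. The same share tied to the protocol's 10% of babies.** With twins only, the twin share of infants is f = 2t/(1 + t), and ps is solved so that the overall rate is 10%.

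- t = 1%, pm = 40%: f = 1.98%, ps = 9.4%. Twins supply 4.1% of preterm pregnancies and 7.9% of preterm infants.
- t = 3%, pm = 60%: f = 5.83%, ps = 6.9%. Twins supply 21.2% of preterm pregnancies and 35.0% of preterm infants.

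Both routes give roughly 4-21% of preterm pregnancies, several times the share of multiples among all pregnancies.

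**Step 3. Bias in an anxiety-preterm risk ratio** = [1 + p1(RR − 1)] / [1 + p0(RR − 1)], where p1 and p0 are the shares of multiples among more and less anxious women, and RR is the preterm risk ratio for multiples.

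- p1 = p0: factor 1.00, whatever the RR
- p1 = 2.5%, p0 = 1.5%, RR = 4: 1.075 / 1.045 = 1.03
- p1 = 4%, p0 = 1%, RR = 8: 1.28 / 1.07 = 1.20

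**Step 4. False-positive rate by simulation.** Setting: 1200 women, preterm rate 55% in multiples and 8% in singletons, no true anxiety effect, nominal 5% level.

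| Anxiety higher in multiples by | 1.5% multiples | 3.5% multiples |
|---|---|---|
| 0 SD | about 5% | about 5% |
| 0.2 SD | 5.1% | 6.6% |
| 0.4 SD | 6.2% | 12.2% |
| 0.6 SD | 8.2% | 20.2% |

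The spurious odds ratio per SD of anxiety is 1.02-1.04 at 0.2 SD and at most about 1.12 in the corner with 3.5% multiples and 0.6 SD.

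Low birthweight and placental outcomes were not quantified, because neither the protocol nor these assumptions supply the rates needed.

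**The case against.** The strongest reply is that confounding needs a link between plurality and anxiety, and the protocol gives none. A reader might infer from the missing covariate that twin pregnancies do confound the anxiety associations. The documents do not support that. With no link, the false-positive rate stays at 5% and the bias factor is 1.00. Even with a link, the bias is small over most of the assumed range. This part of the objection stands.

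A reader might also infer that two infants of one mother will enter as independent records. The protocol does not say so. Section 11.6 works with participants and individual slopes, and section 11.5 counts deliveries, both of which point to the woman as the unit. If separate records were used and twins shared preterm status, the false-positive rate would be 7.3-8.2% even with no anxiety link. That is a reason to state the unit, not evidence that the error will be made.

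The mediation models are adjusted for unnamed covariates, so plurality could enter there. This also stands, but the wording commits to nothing, and the other models name their list without it.

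Purposes 1 and 2, the hypotheses and the sample-size basis concern placental pathology and biomarkers, so much of the study is less exposed. This is accepted.

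Enrolling multiples fits the stated target of all pregnant women. This is also accepted, and enrolment need not change.

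Finally, the analysis population and sensitivity analyses are often left to a statistical analysis plan, which is not at hand. But eligibility and the covariate list are fixed in this protocol, and a model fitted to that list would omit plurality.

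**Conclusion.** The point holds in a limited form. Multiple pregnancies are eligible, plurality is not listed for collection, and it is not among the named covariates. On assumed rates, multiples would supply a disproportionate 4-21% of preterm pregnancies. The certain consequence is added outcome variance in the birth-outcome models. Confounding is conditional on anxiety differing by plurality: the risk-ratio factor runs from 1.00 with no difference to about 1.03-1.20 for the imbalances tried. The higher false-positive rates, up to about 20%, need both a high share of multiples and a large anxiety difference.

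It would go too far to say that multiples dominate the adverse outcomes. The low end of the range is 4%, and no low-birthweight figure is available. The concern bears mainly on purpose 3 and the birth-outcome analyses. It is worth correcting before the data are examined, but it is not fatal to the study.

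**What to change.** 1. Add plurality to the data items in sections 10.1 and 11.1, taken from the obstetric record that participants already authorise the study to access.
2. For the birth-outcome models in section 11.6, including the mediation models, choose one of two lead analyses. Either restrict to singleton pregnancies, or include all women with plurality as a forced covariate exempt from backward elimination. Report the other as a sensitivity analysis.
3. State that the woman is the unit of analysis and how a second infant or placenta is handled. If infants are analysed individually, cluster them on the mother.

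The cost is one data item and a few sentences, with no change to enrolment. If the lead analysis is restricted, at most about 4% of women leave it (42 of 1200, or 3.5%, at the top of the assumed range), and its conclusions then apply to singleton pregnancies rather than to all pregnant women at the site. The forced-covariate option keeps everyone, but the plurality effect would be estimated from as few as 12 women at the low end of the assumed range.
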